## Appendix

03LK4C Z	3953	Occlusion of Right Internal Carotid Artery with Extraluminal Device, Percutaneous Endoscopic Approach	Repair of arteriovenous fistula
03LK4Z Z	3953	Occlusion of Right Internal Carotid Artery, Percutaneous Endoscopic Approach	Repair of arteriovenous fistula
03LL0C Z	3953	Occlusion of Left Internal Carotid Artery with Extraluminal Device, Open Approach	Repair of arteriovenous fistula
03LL0Z Z	3953	Occlusion of Left Internal Carotid Artery, Open Approach	Repair of arteriovenous fistula
03LL3C Z	3953	Occlusion of Left Internal Carotid Artery with Extraluminal Device, Percutaneous Approach	Repair of arteriovenous fistula
03LL3Z Z	3953	Occlusion of Left Internal Carotid Artery, Percutaneous Approach	Repair of arteriovenous fistula
03LL4C Z	3953	Occlusion of Left Internal Carotid Artery with Extraluminal Device, Percutaneous Endoscopic Approach	Repair of arteriovenous fistula
03LL4Z Z	3953	Occlusion of Left Internal Carotid Artery, Percutaneous Endoscopic Approach	Repair of arteriovenous fistula
03PY07 Z	3943	Removal of Autologous Tissue Substitute from Upper Artery, Open Approach	Removal of arteriovenous shunt for renal dialysis
03PY0J Z	3994	Removal of Synthetic Substitute from Upper Artery, Open Approach	Replacement of vessel-to-vessel cannula
03PY0K Z	3943	Removal of Nonautologous Tissue Substitute from Upper Artery, Open Approach	Removal of arteriovenous shunt for renal dialysis
03PY37 Z	3943	Removal of Autologous Tissue Substitute from Upper Artery, Percutaneous Approach	Removal of arteriovenous shunt for renal dialysis
03PY3J Z	3994	Removal of Synthetic Substitute from Upper Artery, Percutaneous Approach	Replacement of vessel-to-vessel cannula
03PY3K Z	3943	Removal of Nonautologous Tissue Substitute from Upper Artery, Percutaneous Approach	Removal of arteriovenous shunt for renal dialysis
03PY47 Z	3943	Removal of Autologous Tissue Substitute from Upper Artery, Percutaneous Endoscopic Approach	Removal of arteriovenous shunt for renal dialysis
03PY4J Z	3994	Removal of Synthetic Substitute from Upper Artery, Percutaneous Endoscopic Approach	Replacement of vessel-to-vessel cannula
03PY4K Z	3943	Removal of Nonautologous Tissue Substitute from Upper Artery, Percutaneous Endoscopic Approach	Removal of arteriovenous shunt for renal dialysis
03VK0C Z	3953	Restriction of Right Internal Carotid Artery with Extraluminal Device, Open Approach	Repair of arteriovenous fistula
03VK3C Z	3953	Restriction of Right Internal Carotid Artery with Extraluminal Device, Percutaneous Approach	Repair of arteriovenous fistula
03VK4C Z	3953	Restriction of Right Internal Carotid Artery with Extraluminal Device, Percutaneous Endoscopic Approach	Repair of arteriovenous fistula
03VL0C Z	3953	Restriction of Left Internal Carotid Artery with Extraluminal Device, Open Approach	Repair of arteriovenous fistula
03VL3C Z	3953	Restriction of Left Internal Carotid Artery with Extraluminal Device, Percutaneous Approach	Repair of arteriovenous fistula
03VL4C Z	3953	Restriction of Left Internal Carotid Artery with Extraluminal Device, Percutaneous Endoscopic Approach	Repair of arteriovenous fistula
03WY0J Z	3994	Revision of Synthetic Substitute in Upper Artery, Open Approach	Replacement of vessel-to-vessel cannula
03WY3J Z	3994	Revision of Synthetic Substitute in Upper Artery, Percutaneous Approach	Replacement of vessel-to-vessel cannula
03WY4J Z	3994	Revision of Synthetic Substitute in Upper Artery, Percutaneous Endoscopic Approach	Replacement of vessel-to-vessel cannula
03WYX JZ	3994	Revision of Synthetic Substitute in Upper Artery, External Approach	Replacement of vessel-to-vessel cannula
05HY33 Z	3895	Insertion of Infusion Device into Upper Vein, Percutaneous Approach	Venous catheterization for renal dialysis
06HY33 Z	3895	Insertion of Infusion Device into Lower Vein, Percutaneous Approach	Venous catheterization for renal dialysis
0TS00Z Z	5561	Reposition Right Kidney, Open Approach	Renal autotransplantation
0TS10Z Z	5561	Reposition Left Kidney, Open Approach	Renal autotransplantation
0TY00Z 0	5569	Transplantation of Right Kidney, Allogeneic, Open Approach	Other kidney transplantation
0TY00Z 1	5569	Transplantation of Right Kidney, Syngeneic, Open Approach	Other kidney transplantation

## Appendix

0TY00Z 2	5569	Transplantation of Right Kidney, Zooplastic, Open Approach	Other kidney transplantation
0TY10Z 0	5569	Transplantation of Left Kidney, Allogeneic, Open Approach	Other kidney transplantation
0TY10Z 1	5569	Transplantation of Left Kidney, Syngeneic, Open Approach	Other kidney transplantation
0TY10Z 2	5569	Transplantation of Left Kidney, Zooplastic, Open Approach	Other kidney transplantation
3E1M39 Z	5498	Irrigation of Peritoneal Cavity using Dialysate, Percutaneous Approach	Peritoneal dialysis
5A1D70 Z	3995	Performance of Urinary Filtration, Intermittent, Less than 6 Hours Per Day	Hemodialysis
5A1D80 Z	3995	Performance of Urinary Filtration, Prolonged Intermittent, 6-18 hours Per Day	Hemodialysis
5A1D90 Z	3995	Performance of Urinary Filtration, Continuous, Greater than 18 hours Per Day	Hemodialysis
Heart Failure Dx			
ICD10	ICD9	ICD10 Description	ICD9 Description
I0981	39891	Rheumatic heart failure	Rheumatic heart failure (congestive)
I110	40291	Hypertensive heart disease with heart failure	Unspecified hypertensive heart disease with heart failure
I130	40491	Hypertensive heart and chronic kidney disease with heart failure and stage 1 through stage 4 chronic kidney disease, or unspecified chronic kidney disease	Hypertensive heart and chronic kidney disease, unspecified, with heart failure and with chronic kidney disease stage I through stage IV, or unspecified
I132	40493	Hypertensive heart and chronic kidney disease with heart failure and with stage 5 chronic kidney disease, or end stage renal disease	Hypertensive heart and chronic kidney disease, unspecified, with heart failure and chronic kidney disease stage V or end stage renal disease
I501	4281	Left ventricular failure, unspecified	Left heart failure
I5020	4280	Unspecified systolic (congestive) heart failure	Congestive heart failure, unspecified
I5021	4280	Acute systolic (congestive) heart failure	Congestive heart failure, unspecified
I5022	4280	Chronic systolic (congestive) heart failure	Congestive heart failure, unspecified
I5023	4280	Acute on chronic systolic (congestive) heart failure	Congestive heart failure, unspecified
I5030	4280	Unspecified diastolic (congestive) heart failure	Congestive heart failure, unspecified
I5031	4280	Acute diastolic (congestive) heart failure	Congestive heart failure, unspecified
I5032	4280	Chronic diastolic (congestive) heart failure	Congestive heart failure, unspecified
I5033	4280	Acute on chronic diastolic (congestive) heart failure	Congestive heart failure, unspecified
I5040	4280	Unspecified combined systolic (congestive) and diastolic (congestive) heart failure	Congestive heart failure, unspecified
I5041	4280	Acute combined systolic (congestive) and diastolic (congestive) heart failure	Congestive heart failure, unspecified
I5042	4280	Chronic combined systolic (congestive) and diastolic (congestive) heart failure	Congestive heart failure, unspecified
I5043	4280	Acute on chronic combined systolic (congestive) and diastolic (congestive) heart failure	Congestive heart failure, unspecified
I50810	4289	Right heart failure, unspecified	Heart failure, unspecified
I50811	4289	Acute right heart failure	Heart failure, unspecified
I50812	4289	Chronic right heart failure	Heart failure, unspecified
I50813	4289	Acute on chronic right heart failure	Heart failure, unspecified
I50814	4280	Right heart failure due to left heart failure	Congestive heart failure, unspecified
I5082	4289	Biventricular heart failure	Heart failure, unspecified
I5083	4289	High output heart failure	Heart failure, unspecified
I5084	4289	End stage heart failure	Heart failure, unspecified
I5089	4289	Other heart failure	Heart failure, unspecified
I509	4289	Heart failure, unspecified	Heart failure, unspecified
Hypotension Dx			
ICD10	ICD9	ICD10 Description	ICD9 Description
I950	4581	Idiopathic hypotension	Chronic hypotension
I951	4580	Orthostatic hypotension	Orthostatic hypotension
I953	45821	Hypotension of hemodialysis	Hypotension of hemodialysis
I9589	4588	Other hypotension	Other specified hypotension
I959	4589	Hypotension, unspecified	Hypotension, unspecified
I952	45829	Hypotension due to drugs	Other iatrogenic hypotension
I9581	45829	Postprocedural hypotension	Other iatrogenic hypotension
Hyperkalemia Dx			
ICD10	ICD9	ICD10 Description	ICD9 Description
E875	2767	Hyperkalemia	Hyperpotassemia

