## STUDY POPULATION

1. Study population (see Figure 2) is created for each calendar interval.
2. Initiation of ARNI or comparator (ARB)
  - a. ARB: any of azilsartan, candesartan, eprosartan, Irbesartan, losartan, Olmesartan, telmisartan, valsartan
  - b. Index date (day 0): prescription fill from July 7, 2015

3. Assessment of eligibility (eligibility assessment window: [-365, 0] days) – See Appendix for list of codes.
  - a. Continuous enrollment for medical and drug insurance (Part A, B, and D)
  - b. Diagnosis of HF (outpatient diagnosis x2 or inpatient x1)
  - c. Reduced EF (<45%) algorithm (5)
  - d. No prior use of ARNI or comparator (exposure wash-out window: [-365, -1] days)
  - e. No recent HF hospitalization, defined as HF diagnosis (Appendix) in the primary position in the inpatient dataset (outcome wash-out window: [-60, 0] days)
  - f. No recent nursing facility stay, defined as any of the following claims in [-60, 0] days
    - i. Place of service: 31 (skilled nursing facility), 32 (nursing facility), 33 (custodial care facility)
    - ii. CPT codes: 99301, 99302, 99303, 99311, 99312, 99313, 99315, 99316, 99379, 99380, G0066
  - g. Excluded if age <65 years or exposure to both drugs on day 0
  - h. Contraindication to either drug (exclusion assessment window: [-60, 0] days, unless specified otherwise)
    - i. Hypotension
    - ii. Chronic kidney disease stage IV or V or dialysis
    - iii. Acute kidney injury
    - iv. Hyperkalemia
    - v. Angioedema: [-beginning of data, 0] days
  - i. If a patient meets the above-mentioned eligibility criteria more than once, only the first record will be included.

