## Appendix

Acute kidney injury Dx			
ICD10	ICD9	ICD10 Description	ICD9 Description
I120	40391	Hypertensive chronic kidney disease with stage 5 chronic kidney disease or end stage renal disease	Hypertensive chronic kidney disease, unspecified, with chronic kidney disease stage V or end stage renal disease
N170	5845	Acute kidney failure with tubular necrosis	Acute kidney failure with lesion of tubular necrosis
N171	5846	Acute kidney failure with acute cortical necrosis	Acute kidney failure with lesion of renal cortical necrosis
N172	5847	Acute kidney failure with medullary necrosis	Acute kidney failure with lesion of renal medullary [papillary] necrosis
N178	5848	Other acute kidney failure	Acute kidney failure with other specified pathological lesion in kidney
N179	5849	Acute kidney failure, unspecified	Acute kidney failure, unspecified
N19	586	Unspecified kidney failure	Renal failure, unspecified
Z4931	V560	Encounter for adequacy testing for hemodialysis	Encounter for extracorporeal dialysis
Angioedema Dx			
ICD10	ICD9	ICD10 Description	ICD9 Description
T783XX9951		Angioneurotic edema, initial encounter	Angioneurotic edema, not elsewhere classified
T783XX1V5889		Angioneurotic edema, subsequent encounter	Other specified aftercare
T783XX99099		Angioneurotic edema, sequela	Late effect of other and unspecified external causes
Chronic kidney disease stage IV or V or dialysis Dx			
ICD10	ICD9	ICD10 Description	ICD9 Description
E1021	25043	Type 1 diabetes mellitus with diabetic nephropathy	Diabetes with renal manifestations, type I [juvenile type], uncontrolled
E1022	25041	Type 1 diabetes mellitus with diabetic chronic kidney disease	Diabetes with renal manifestations, type I [juvenile type], not stated as uncontrolled
E1029	25041	Type 1 diabetes mellitus with other diabetic kidney complication	Diabetes with renal manifestations, type I [juvenile type], not stated as uncontrolled
E1065	25043	Type 1 diabetes mellitus with hyperglycemia	Diabetes with renal manifestations, type I [juvenile type], uncontrolled
E1121	25042	Type 2 diabetes mellitus with diabetic nephropathy	Diabetes with renal manifestations, type II or unspecified type, uncontrolled
E1122	25040	Type 2 diabetes mellitus with diabetic chronic kidney disease	Diabetes with renal manifestations, type II or unspecified type, not stated as uncontrolled

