I132	40493	Hypertensive heart and chronic kidney disease with heart failure and with stage 5 chronic kidney disease, or end stage renal disease	Hypertensive heart and chronic kidney disease, unspecified, with heart failure and chronic kidney disease stage V or end stage renal disease
N181	5851	Chronic kidney disease, stage 1	Chronic kidney disease, Stage I
N182	5852	Chronic kidney disease, stage 2 (mild)	Chronic kidney disease, Stage II (mild)
N183	5853	Chronic kidney disease, stage 3 (moderate)	Chronic kidney disease, Stage III (moderate)
N184	5854	Chronic kidney disease, stage 4 (severe)	Chronic kidney disease, Stage IV (severe)
N189	5859	Chronic kidney disease, unspecified	Chronic kidney disease, unspecified
N250	5880	Renal osteodystrophy	Renal osteodystrophy
N251	5881	Nephrogenic diabetes insipidus	Nephrogenic diabetes insipidus
N2581	58881	Secondary hyperparathyroidism of renal origin	Secondary hyperparathyroidism (of renal origin)
N2589	58889	Other disorders resulting from impaired renal tubular function	Other specified disorders resulting from impaired renal function
N259	5889	Disorder resulting from impaired renal tubular function, unspecified	Unspecified disorder resulting from impaired renal function
End-Stage Renal Disease (ESRD) Dx			
ICD10	ICD9	ICD10 Description	ICD9 Description
I953	45821	Hypotension of hemodialysis	Hypotension of hemodialysis
N185	5855	Chronic kidney disease, stage 5	Chronic kidney disease, Stage V

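### The Appendix code list for the stage IV/V kidney-disease exclusion is wider than criterion 3.h.ii; through I130/40491 it removes heart-failure patients with CKD stages 1 to 3 or unstaged CKD

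*Protocol*

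**What the plan says.** Study Population item 3 of the protocol makes the Appendix operative for eligibility: "See Appendix for list of codes". Four parts matter here.

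- **Entry (3.b).** "Diagnosis of HF (outpatient diagnosis x2 or inpatient x1", assessed over days -365 to 0.
- **Wash-out (3.e).** "No recent HF hospitalization, defined as HF diagnosis (Appendix) in the primary position in the inpatient dataset", over days -60 to 0.
- **Exclusion (3.h.ii).** "Chronic kidney disease stage IV or V or dialysis", under the general rule "Contraindication to either drug (exclusion assessment window: [-60, 0] days, unless specified otherwise". Only angioedema is given a different window.
- **Code lists.** The Appendix list headed "Chronic kidney disease stage IV or V or dialysis Dx" contains I130/40491, "Hypertensive heart and chronic kidney disease with heart failure and stage 1 through stage 4 chronic kidney disease, or unspecified chronic kidney disease". The Heart Failure Dx list contains the same code pair with the same description. No text exempts the code from either list.

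**The concern.** The criterion sets a threshold at stage IV. The list that implements it does not. I130 covers CKD from stage 1 to stage 4 and CKD with no stage given, so the code alone cannot show that a patient meets 3.h.ii. Because I130 is also a heart-failure diagnosis, the excess falls directly on the target population: some patients whose heart failure is recorded with this code shortly before the index date leave the cohort although the criterion, as worded, keeps them.

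At stake are the size of the cohort and whom it represents. Heart-failure patients with mild, moderate or unstaged CKD plausibly have more kidney injury and hyperkalemia, both components of the primary safety endpoint. Losing them would cost safety events and weaken applicability to older and frail patients. The protocol lists chronic kidney disease, without stage, in Table 2 as a covariate, which suggests that CKD below the threshold was expected in the cohort.

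**Working it through.** No figure in the protocol can be reproduced here. The check compares the code lists and then applies the windows.

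**1. Overlap of the lists.** The Heart Failure Dx list and the CKD list each hold 27 ICD-10 codes. They share two: I130 and I132 (ICD-9 40491 and 40493). I132 reads "Hypertensive heart and chronic kidney disease with heart failure and with stage 5 chronic kidney disease, or end stage renal disease", so excluding on it agrees with 3.h.ii. I130 reaches below the threshold.

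**2. The 27 ICD-10 codes on the CKD list, sorted by their printed descriptions.**

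- Name stage 4 or stage 5/end-stage disease specifically: N184, I120, I1311, I132. That is 4.
- Span stages 1 to 4 or unspecified: I129, I130, I1310. That is 3.
- Name neither stage IV, stage V nor dialysis: 11 diabetes codes (E1021 to E1329), N181, N182, N183, N189, and 5 codes from N250 to N259. That is 11 + 4 + 5 = 20.

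Total: 4 + 3 + 20 = 27. In the third group, N181 to N183 are explicitly stages 1 to 3, and the ICD-10 descriptions of E1065 and E1165 mention hyperglycemia but no kidney disease. Stage 5 (N185/5855) and dialysis dependence (Z992/V4511) stand on the separate End-Stage Renal Disease Dx list. I take that list to serve 3.h.ii as well, since no other criterion uses it.

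**3. The windows applied to I130.** The protocol does not say how many claims trigger an exclusion; one is assumed.

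- Outpatient I130 on day -61: counts toward 3.b and does not trigger 3.h.ii.
- Outpatient I130 on day -60: counts toward 3.b and triggers 3.h.ii, whatever the stage.
- Non-primary inpatient I130 from day -60 to 0: same result.
- Primary-position inpatient I130 from day -60 to 0: already removed by 3.e, so the CKD list adds nothing.

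**4. What I130 adds to the list as it stands.** A patient with an I50 heart-failure code and N183 in the window is also out, through N183. I130 therefore changes the outcome only for patients with an outpatient or non-primary I130 claim in the window, no other listed exclusion code, and CKD that is in fact below stage IV. The protocol gives no count or prevalence for this group.

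**The case against.** **Presence on both lists is not the defect.** A reader might infer that a code cannot both qualify and exclude. It can: entry and exclusion are separate rules, and I132 is on both lists without conflict. What stands is narrower: the description of I130 extends below the threshold in 3.h.ii.

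**I130 is one instance of a wider problem.** This is correct. With 20 other codes naming neither stage IV, stage V nor dialysis, correcting I130 alone would leave many of the same patients excluded. It still deserves specific mention. It is a heart-failure diagnosis, and because its description mentions stage 4 it would pass a check that merely looks for stage IV in the wording.

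**A large loss might be inferred from assumed prevalences.** Suppose 30% to 50% of candidates have CKD, 15% to 20% of those are stage IV/V or on dialysis, and 30% to 80% of the rest have an I130 claim in the window. The share touched is then 0.30 x 0.80 x 0.30 = 7% to 0.50 x 0.85 x 0.80 = 34%. None of these inputs is in the protocol. The product is also a gross share: it subtracts neither the patients removed by 3.e nor those removed by other listed codes. It does not measure what I130 adds, and any loss of safety events derived from it has the same weakness.

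**A biased hazard ratio might be inferred.** The documents do not support this. The exclusion is a baseline rule applied identically to both arms before matching. That a primary-position I130 admission can still count as an outcome is no flaw either, since 3.e deliberately sets up the same arrangement for every heart-failure code.

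**A broad list is more sensitive for a listed contraindication.** This stands as a trade-off. I130 includes stage 4, and nothing in the protocol shows that N184 is always coded beside it. The propensity-score covariate gives only partial reassurance, because Table 2 lists CKD without stage and its source is a Medicare file, while two other databases are also used.

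**Conclusion.** The point holds as an inconsistency between criterion 3.h.ii and its code list, of which I130/40491 is the instance that falls directly on heart-failure patients. Followed as written, the plan removes some patients with stage 1 to 3 or unstaged CKD whom the criterion retains. The consequence is lost precision and narrower applicability. The size is unknown and cannot be derived from the protocol. The conclusion rests on three readings: the Appendix lists are the operating definitions, one claim is enough to exclude, and the End-Stage Renal Disease list also serves 3.h.ii. The correction is worth making because it is cheap and restores the protocol's own threshold.

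**What to change.** Reconcile the Appendix list with 3.h.ii in a single edit:

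1. Let I130/40491, I129/40390 and I1310/40490 exclude only when a stage IV, stage V or dialysis code (such as N184/5854, N185/5855 or Z992/V4511) is also recorded in the exclusion window.
2. Remove the codes that do not denote stage IV, stage V or dialysis, such as N181 to N183, N189, E1065 and E1165. Without this step the first one gains little.
3. Keep I132/40493, I1311/40492 and I120/40391 as exclusions, since they name stage 5.
4. Keep I130/40491 on the Heart Failure Dx list.
5. State how many claims trigger an exclusion, and report the number of patients removed under the current and the edited list. That supplies the size the protocol cannot give.

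If the wider exclusion was intended, 3.h.ii should be reworded to say so.

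The cost is a code-list edit and a re-run of cohort selection and matching, with no new data. The downside is that some stage IV patients recorded only with I130, and without N184, would enter; their number is not known.

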## **STUDY OVERVIEW AND DESIGN**

- 1. Study aims: To emulate a prospective surveillance of the effectiveness and safety of ARNI vs a comparator (ARB) in older adults with HFrEF and different frailty status.
- 2. Data source(s): Data from 2014 up to 2020 will be used.
  - a. Medicare Database
  - b. Optum Database
  - c. MarketScan Research Database
- 3. Sequential cohort monitoring design (see Figure 1): The monitoring analysis will include 1) retrospective analysis of available data (2015-2017) at the time of first analysis (January 2021) and 2) prospective analysis of new data (2018-2020) as they become available to the researchers. Within each database, we will emulate biannual updating of data by creating a propensity score (PS)-matched cohort of new users every 6-month interval, beginning on the first marketing of ARNI (July 7, 2015-December 31, 2015, and 6-month intervals afterwards). Each sequential cohort will be followed for development of the outcomes of

interest. Outcome analysis will be performed at a pre-specified 6-month interval (prospective analysis). The surveillance will be performed by frailty status (frail vs non-frail) at the time of drug initiation. The results from each database will be pooled using fixed-effects meta-analysis (assuming low heterogeneity across the databases).

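### The ICD-9 half of the Appendix heart-failure list has no systolic, diastolic or combined code, so heart failure is under-captured, by an unknown amount, mainly in the first surveillance interval

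*Protocol*

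**What the plan says.** The Heart Failure Dx table in the Appendix has 27 ICD-10 rows, each with one ICD-9 partner. The systolic rows (for example "Acute systolic (congestive) heart failure"), the diastolic rows and the combined rows (for example "Acute on chronic combined systolic (congestive) and diastolic (congestive) heart failure") all carry 4280 as partner, described as congestive failure of unspecified type.

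The table is binding on the study rules:

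- STUDY POPULATION, item 3, refers to the Appendix for its codes and sets the "eligibility assessment window: [-365, 0] days". Rule 3.b requires "Diagnosis of HF (outpatient diagnosis x2 or inpatient x1".
- Rule 3.e, the 60-day wash-out, names the list directly: "No recent HF hospitalization, defined as HF diagnosis (Appendix) in the primary position in the inpatient dataset".
- MEASUREMENTS, Outcomes, defines the HF-hospitalization component of the primary effectiveness endpoint in the same way, by an HF diagnosis in primary inpatient position.
- STATISTICAL ANALYSIS, item 3.g, forms a subgroup by the number of HF hospitalizations in the past year.

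On timing, STUDY OVERVIEW AND DESIGN states "Data from 2014 up to 2020 will be used" and creates cohorts "beginning on the first marketing of ARNI (July 7, 2015-December 31, 2015, and 6-month intervals afterwards". STUDY POPULATION gives "Index date (day 0): prescription fill from July 7, 2015".

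**The concern.** The study begins while US claims were still coded in ICD-9, which is presumably why the Appendix carries both systems. If ICD-9 had its own codes for typed heart failure, the two halves of the list do not select the same patients: the ICD-10 half captures typed and untyped failure, the ICD-9 half only the untyped codes and a few others.

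Three things are at stake in the launch period.

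- **Wash-out.** A patient admitted with a typed ICD-9 code in primary position within 60 days of the index date is not removed by 3.e. The covariates listed under MEASUREMENTS do not name recent HF admission, so matching is not specified to balance what gets through.
- **Outcome.** The same kind of admission after the index date is not counted as an HF hospitalization.
- **Entry.** A patient whose claims carry mainly typed ICD-9 codes may fail 3.b. One who stays on treatment is not simply picked up at a later fill, because 3.d excludes use of either drug in the previous 365 days.

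The meaning of these rules would therefore shift between the launch cohorts and the later ones in a single surveillance series.

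**Working it through.** The protocol gives no figure to reproduce. The check is a count of the table followed by date arithmetic.

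**Step 1. Count the table (Appendix, Heart Failure Dx).**

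- ICD-10 rows: 27.
- Distinct ICD-9 codes: 7 (39891, 40291, 40491, 40493, 4280, 4281, 4289).
- Type-specific ICD-10 rows: I5020–I5023, I5030–I5033 and I5040–I5043, so 3 × 4 = 12. ICD-9 partner in all twelve: 4280.
- ICD-9 codes beginning 4282, 4283 or 4284: 0.

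Matching on the stem 4280 would not pick up 4282x–4284x, since it is not a prefix of them. Nor is coarse pairing the rule elsewhere in the Appendix: N181–N184 are matched to 5851–5854 stage by stage, and I953 to 45821.

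**Step 2. Assumptions not in the protocol.** ICD-9-CM has 428.2x (systolic), 428.3x (diastolic) and 428.4x (combined). US claims changed to ICD-10 on October 1, 2015. Index dates are spread evenly within each interval.

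**Step 3. ICD-9 share of each look-back.** The window [-365, 0] has 366 days and [-60, 0] has 61.

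*Interval 1 (July 7 to December 31, 2015).* Index days: 25 + 31 + 30 = 86 before the changeover and 31 + 30 + 31 = 92 after, total 178. For the first 86 (86/178 = 48%) both windows lie wholly in ICD-9 time. After that each index day loses one ICD-9 day.

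- 365-day window: (86 × 366 + 92 × 366 − 92 × 93/2) / (178 × 366) = (31,476 + 33,672 − 4,278) / 65,148 = 60,870 / 65,148 = 93%.
- 60-day window: (86 × 61 + 60 × 61/2) / (178 × 61) = (5,246 + 1,830) / 10,858 = 65%.

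*Interval 2 (January to June 2016).* ICD-9 days in the 365-day window fall from 273 to 92, mean 182.5, and 182.5/366 = 50%. The 60-day window contains none.

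*Interval 3 (July to December 2016, 184 index days).* ICD-9 days fall from 91 on July 1 to 1 on September 29, then 0. The mean share is (91 × 92/2) / (184 × 366) = 4,186 / 67,344 = 6%, and never more than 91/366 = 25%.

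**Step 4. Last affected dates.**

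| Rule | Calculation | Last affected date |
|---|---|---|
| 3.b entry | September 30, 2015 + 365 days (2016 is a leap year) | index date September 29, 2016 |
| 3.e wash-out | September 30, 2015 + 60 days | index date November 29, 2015 |
| HF-hospitalization outcome | July 8 to September 30, 2015: 24 + 31 + 30 | event date September 30, 2015 (85 days) |

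**Step 5. How each rule fails.** Rule 3.e and the outcome need the HF code in primary position, so an admission with primary 428.2x is missed even if 4280 is a secondary code. Rule 3.b has no primary-position requirement and can be met by any listed code over a year, so it fails only for patients without enough other listed codes. A patient wrongly passes 3.e only if other listed codes satisfy 3.b. The entry loss and the wash-out leak therefore fall on different patients.

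**The case against.** The strongest objection is about sourcing. The protocol never says that ICD-9 has typed HF codes or when ICD-9 ended, and without those facts the table shows only many rows mapped to one unspecified code. That stands to the extent that both must be labelled as assumptions. They are basic facts of the code sets, however, and the typed-to-unspecified pairing is visible on the page.

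A second objection is that the table may be an incomplete crosswalk, not a deliberate definition. Z4931, for example, is paired with V560 under acute kidney injury and with V5631 under end-stage renal disease. That is plausible, but the protocol makes this table the operative list, so the gap needs closing whatever its origin.

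Other objections limit the point, and they stand. A reader might infer that the list shuts out the HFrEF patients the study is about. The protocol does not support that: reduced ejection fraction is a separate rule (3.c) with its own cited algorithm, the missing codes include diastolic as well as systolic failure, and patients with enough other listed codes still enter. Rule 3.c cannot rescue anyone who fails 3.b, but the result is under-capture, not exclusion of the group. A reader might also count three of the eleven intervals as damaged, although the third has on average 6% ICD-9 look-back and no wash-out or outcome effect.

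Finally, both arms use the same list, and propensity scores are fitted and matched within each cohort, so a definition that shifts between cohorts does not by itself confound the comparison within a cohort.

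**Conclusion.** The ICD-9 side of the heart-failure list is incomplete and should be corrected. Under the two coding assumptions, admissions with a type-specific primary ICD-9 code are invisible to the wash-out and to the HF-hospitalization component in the early months, and some patients fail the HF diagnosis rule. The effect is mainly in interval 1, partly in interval 2 (entry, and the prior-year HF-hospitalization subgroup if it uses this list), and negligible in interval 3.

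The number of patients or events affected cannot be computed, because the protocol gives no share of HF claims with typed codes. Nor does it support a claim that the primary endpoint as a whole is lost in that period, since its all-cause death component does not depend on this list, or that early users of either drug are selectively missed. The direction of any bias in the hazard ratio is unknown. The point is confined in time, but it touches entry, wash-out and one component of the primary endpoint, and the earliest looks of the sequential monitoring rest on these cohorts.

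**What to change.** Add 428.20–428.23, 428.30–428.33 and 428.40–428.43 opposite I5020–I5023, I5030–I5033 and I5040–I5043 in the Heart Failure Dx table. State that the corrected list governs rules 3.b and 3.e, the HF-hospitalization endpoint and the prior-year HF-hospitalization subgroup. Give the ICD-9 to ICD-10 changeover date used. Then re-run cohort creation, matching and outcome capture for the affected launch cohorts.

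The cost is twelve codes in one table and a re-run on data already held. If the programmed list already contains these codes, only the Appendix needs correcting.
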